## 6.6. STATISTICAL TESTS

No statistical testing will be done.

## 6.7. COMMON CALCULATIONS

For quantitative measurements, change from baseline at Visit X will be calculated as:

Test Value at Visit X – Baseline Value

Document:

[REDACTED]

Author:

[REDACTED]

Version Number:

2.0

Version Date:

23APR2024

Template No.: CS\_TP\_BS016 Revision 6

Reference: CS\_WI\_BS005

Effective Date: 02Dec2019

Copyright © 2009, 2010, 2012, 2016, 2018, 2019 [REDACTED]. All rights reserved. The contents of this document are confidential and proprietary to [REDACTED] and its subsidiaries. Unauthorized use, disclosure or reproduction is strictly prohibited.

## 6.8. SOFTWARE VERSION

All analyses will be conducted using SAS version 9.4 or higher.

## 7. STATISTICAL CONSIDERATIONS

### 7.1. HANDLING OF MISSING AND INCOMPLETE DATA

Partial or missing dates for AEs and medications will be imputed as described in section 16 Appendix A of this SAP.

Missing safety data will not be imputed.

An estimated date of conception is required from the investigator for all pregnancies and will be recorded in the eCRF. If the estimated date of conception cannot be determined, the pregnancy diagnosis and first/last dose date will be used to define a pregnancy as pre-treatment, on-treatment, or post-treatment.

## 8. OUTPUT PRESENTATIONS

Conventions for presentation of data in outputs will be included in the Programming Conventions for Outputs document.

The templates provided with this SAP describe the presentations for this study and therefore the format and content of the summary tables, figures, and listings to be provided by [REDACTED] Biostatistics.

All data will be listed, and summary tables will be provided. Continuous variables will be summarized for the measured values and change from baseline values using the number of observations, mean, standard deviation, median, minimum, and maximum. Categorical variables will be summarized with counts and percentages for each category.

---

Document: [REDACTED]

Author: [REDACTED]

Version Number:

2.0

Version Date:

23APR2024

Template No.: CS\_TP\_BS016 Revision 6

Reference: CS\_WI\_BS005

Effective Date: 02Dec2019

Copyright © 2009, 2010, 2012, 2016, 2018, 2019 [REDACTED]. All rights reserved. The contents of this document are confidential and proprietary to [REDACTED] and its subsidiaries. Unauthorized use, disclosure or reproduction is strictly prohibited.

## 9. DISPOSITION AND WITHDRAWALS

All participants who provided informed consent will be accounted for in this study.

### 9.1. DISPOSITION

Participant disposition and withdrawals, and reasons for exclusion from each analysis set will be presented for the ENR set.

The number and percentage of participants who were screened, screen failed (including reason screen failed), allocated to treatment, completed or discontinued the Treatment Period (including reasons for early treatment discontinuation), and completed or withdrew from the study (including reasons for study withdrawal) will be presented. In addition, the primary reason for discontinuation for participants who were allocated to study treatment but discontinued prior to study treatment (non-treated participants) will be presented. Completion of treatment and completion of study are recorded on the End of Study Treatment and Disposition eCRFs, respectively.

### 9.2. PROTOCOL DEVIATIONS

The [REDACTED] Clinical Trial Management System (CTMS) will collect protocol deviations and as per the Protocol Deviation Management Plan, where deviations will be assigned a clinical categorization of ‘Critical/Major/Minor’ and will be deemed as Important or not. To reduce potential bias from the review, participant ID and site ID will be hidden during review. All major and critical protocol deviations will be summarized for the SAF.

## 10. DEMOGRAPHIC AND OTHER BASELINE CHARACTERISTICS

Demographics and baseline characteristics include age (years), race, ethnicity (Hispanic or Latino), body weight (kg), height (cm), and BMI (kg/m^2). All variables will be summarized by descriptive statistics for the SAF populations. Substance use will be listed. BMI will be calculated in EDC as follows:

$$\text{BMI (kg/m}^2\text{)} = \text{weight (kg)}/ \text{height (m)}^2$$

---

Document: [REDACTED]

Author: [REDACTED]

Version Number:

2.0

Version Date:

23APR2024

Template No.: CS\_TP\_BS016 Revision 6

Reference: CS\_WI\_BS005

Effective Date: 02Dec2019

Copyright © 2009, 2010, 2012, 2016, 2018, 2019 [REDACTED]. All rights reserved. The contents of this document are confidential and proprietary to [REDACTED] and its subsidiaries. Unauthorized use, disclosure or reproduction is strictly prohibited.

## 11. MEDICAL, GYNECOLOGICAL, AND CONTRACEPTIVE HISTORY

General medical history, gynecological and obstetric history, contraceptive history, and contraceptive status at Visit 1 and Visit 2 will be presented for the SAF population.

### 11.1. GENERAL MEDICAL HISTORY

Medical history will be coded using Medical Dictionary for Regulatory Activities (MedDRA) version 26.1 or higher. Medical history conditions are defined as relative conditions which are reported at screening and may or may not be ongoing as of the screening visit. Medical history will be listed using System Organ Class (SOC) and Preferred Term (PT).

### 11.2. GYNECOLOGICAL AND OBSTETRIC HISTORY

For the gynecological history, the time since menarche (in years) will be summarized, as well as the usual duration of menstrual flow (in days) and usual volume of flow without hormonal contraceptive use.

Information relative to the pregnancy history will present the number and percentage of study participants with previous pregnancies as well as descriptive statistics for the overall number of previous pregnancies (gravidity number) and the number of times the participant has given birth to a fetus with gestational age of 24 weeks or more (parity number).

### 11.3. CONTRACEPTIVE HISTORY

For the contraceptive history at Visit 1, the number and percentage of participants who have previously used a medical or barrier method of contraception in the 6 months prior to screening will be presented. The frequency of participants who used any of the following will also be presented: male condom, female condom, cervical cap, diaphragm, vaginal sponge, vaginal ring, vaginal spermicides, emergency contraceptive pills, contraceptive patch, contraceptive ring, contraceptive implant, contraceptive injection (overall and separately for 1 month, 2 months, and 3 months duration), combined oral contraceptive, progestin-only oral contraceptive, intrauterine device with/without hormone, or other contraceptive.

---

Document: [REDACTED]

Author: [REDACTED]

Version Number:

2.0

Version Date:

23APR2024

Template No.: CS\_TP\_BS016 Revision 6

Reference: CS\_WI\_BS005

Effective Date: 02Dec2019

Copyright © 2009, 2010, 2012, 2016, 2018, 2019 [REDACTED]. All rights reserved. The contents of this document are confidential and proprietary to [REDACTED] and its subsidiaries. Unauthorized use, disclosure or reproduction is strictly prohibited.

The contraceptive status at Visit 1 will be summarized in the same manner as contraceptive history. The contraceptive history will be presented for the SAF.

## 12. MEDICATIONS

Medications will be presented for the SAF population and coded using WHODrug Global B3 version 01March2023 or later; additional populations will be summarized as noted below.

See Appendix A for handling of partial dates for medications, in the case where it is not possible to define a medication as prior, concomitant, or post treatment, the medication will be classified by the worst case; i.e. concomitant.

- ‘Prior’ medications are medications that started prior to the first dose of study treatment.
- ‘Concomitant’ medications are medications that started on or after the first dose of study treatment and started no later than 7 days following end of study treatment, with the exception that medications for contraceptive use after the end of study treatment will be excluded.
- ‘Post’ medications are medications that started more than 7 days following the last dose of study treatment, with the exception that all medications for contraceptive use starting any day after last dose of study treatment will be included.

Prior/concomitant/post-treatment medication use will be listed using preferred name and Anatomical Therapeutic Chemical (ATC) Level 3. If a medication is unable to be categorized to ATC Level 3, the most detailed level available will be used.

## 13. STUDY TREATMENT EXPOSURE

Exposure to study treatment in days will be presented for the SAF population. The date of first study treatment administration will be taken from the Drug Accountability eCRF. The date of last study treatment is taken from e-Diary.

Duration of exposure (days) = date of last study treatment administration – date of first study treatment administration + 1.

---

Document: [REDACTED]

Author: [REDACTED]

Version Number:

2.0

Version Date:

23APR2024

Template No.: CS\_TP\_BS016 Revision 6

Reference: CS\_WI\_BS005

Effective Date: 02Dec2019

Copyright © 2009, 2010, 2012, 2016, 2018, 2019 [REDACTED] All rights reserved. The contents of this document are confidential and proprietary to [REDACTED] and its subsidiaries. Unauthorized use, disclosure or reproduction is strictly prohibited.

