6.2 Preparation/Handling/Storage/Accountability

The Investigator, a member of the study site staff, or a hospital pharmacist must maintain an adequate record of the receipt and distribution of all study drug using the Drug Accountability Form. These forms must be available for inspection at any time.

The Investigator or designee must confirm appropriate temperature conditions have been maintained during transit for all study treatment received and any discrepancies are reported and resolved before use of the study treatment.

Only eligible participants in the study may receive study treatment and only authorized site staff may supply or administer study treatment. All study treatment must be stored in a secure,

environmentally controlled, and monitored (manual or automated) area in accordance with the labeled storage conditions with access limited to the Investigator and authorized site staff.

The Investigator, institution, or the head of the medical institution (where applicable) is responsible for study treatment accountability, reconciliation, and record maintenance (ie, receipt, reconciliation, and final disposition records).

Study site personnel will be responsible for the assessment of drug accountability, by counting returned blisters and unused tablets during on-site visits, which must be documented in the source documents and relevant form.

A record of the quantity of blisters dispensed to and blisters administered by each participant must be maintained and reconciled with study drug records. Study drug start and stop dates will also be recorded in the e-Diary and eCRF.

For reporting of potential quality-related issues with blister, refer to the Pharmacy Manual.

Further guidance and information for the final disposition of unused study drugs are provided in the Pharmacy Manual or other specified location.

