8.2.3.1.1 Daily e-Diary Questions

Every day, starting at V2, eligible participants are to record the intake of study drug during the past 24 hours.

Every day, starting at V1, participants are to record vaginal bleeding-spotting events that occurred during the past 24 hours. The use of any sanitary products (ie, tampons, pads, panty liners, or menstrual cup), used for vaginal bleeding should be recorded. Other sanitary products that do not permit the estimation of the amount of bleeding (eg, superabsorbent undergarments) should not be used. Sanitary products that are used for any other reason (eg, for urinary incontinence or vaginal discharge) are not recorded in the e-Diary. The questions should be completed EVERY DAY until V7 to also cover the withdrawal period, so that scheduled bleeding after the last cycle can also be determined.

Participants should alert the site immediately if they are experiencing technical difficulties with their e-Diary. The e-Diary will allow daily data entry up to 24 hours late, after which, data entry will be locked out. Participants should complete the e-Diary entry before returning their device at V7.

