8.2.3.1.3 Monitoring e-Diary Compliance

e-Diary entries will be uploaded daily and monitored for completion. The e-Diary is equipped with a sound alert to daily remind participants to complete the e-Diary. Participants will receive a daily reminder alert to complete the e-Diary. Participants will not receive a daily reminder to take study drug. Compliance will be remotely monitored by study staff on an ongoing basis and will be reviewed at each site visit and phone contact.

Missing daily e-Diary entries will interfere with the interpretation of adherence to study drug intake and the vaginal bleeding profile. Sites will be contacted if 2 consecutive daily e-Diary entries are missing. When alerted to missing entries, the site is expected to contact the participant in a timely fashion and remind the participant to complete the e-Diary. Attempts to contact the participant should be documented within the study record.

As the end of cycle questions (to be answered before starting a new blister) regarding heterosexual vaginal intercourse and additional contraceptive use are crucial to the primary efficacy endpoints (and missing data will result in the exclusion of a cycle from the primary endpoint PI calculation), at the time of the statistical analysis, missing end of cycle e-Diary entries will be imputed by 'No' for heterosexual vaginal intercourse and 'Yes' for use of additional contraception, making the cycle to be considered not at-risk, which will exclude the entire cycle for the primary contraceptive efficacy analysis (unless a pregnancy occurred).

At all site visits, compliance with daily and end of cycle e-Diary entries will be reviewed by site staff. Reinforcement of e-Diary study requirements and additional e-Diary training will be provided to study participants, as needed. Additional study visits may also be scheduled to provide additional training as needed for participants who continue to fill out the e-Diary incorrectly or incompletely. Participants who are not compliant should be re-trained.

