## 14. STUDY TREATMENT COMPLIANCE

Compliance with the use of study treatment will be presented for the SAF population. The intake of study treatment will be recorded daily in the e-Diary. The e-Diary will be the primary source for the calculation of compliance with the use of study treatment.

Non-compliance to study treatment intake within a cycle is defined as 4 or more days with forgotten tablets, or 2 or more consecutive days with forgotten tablets.

- Overall Compliance to study treatment will be calculated as following:

$$\frac{\text{Number of days that at least one tablet was taken in the treatment period, as per e-Diary}}{[\text{Date of last dose} - \text{date of first dose} + 1]} \times 100$$

In addition, the number and percentage of participants who took 3 or more tablets on a given day, which is considered as an overdose, will be presented. Number of participants (and cycles) with evaluable cycles will be tabulated and listed.

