### 15.1. ADVERSE EVENTS

AEs will be coded using MedDRA coding dictionary, Version 26.1 or higher.

Treatment-emergent adverse events (TEAEs) are defined as AEs that started on or after the day of first dose of study treatment (or worsened in severity) and prior to the last date of study treatment + 14 days (inclusive). See Appendix A for handling of partial dates for AEs. In the case where it is not possible to define an AE as treatment emergent or not due to a partial start date, the AE will be classified by the worst case; i.e. treatment emergent. Pre-treatment AEs/SAEs starting before the on-treatment period, including those starting on the day of first dose of study treatment yet prior to the study treatment intake, will be excluded from the TEAE analyses. Pre- and post-treatment AEs will be identified in listings.

---

Document: [REDACTED]

Author: [REDACTED]

Version Number:

2.0

Version Date:

23APR2024

Template No.: CS\_TP\_BS016 Revision 6

Reference: CS\_WI\_BS005

Effective Date: 02Dec2019

Copyright © 2009, 2010, 2012, 2016, 2018, 2019 [REDACTED]. All rights reserved. The contents of this document are confidential and proprietary to [REDACTED] and its subsidiaries. Unauthorized use, disclosure or reproduction is strictly prohibited.

An overview table of number (%) of participants within each of the categories described in the sub-section below will be provided as specified in the templates. The broad AE categories consisting of the percentage of participants with any TEAE, a drug-related TEAE, a serious TEAE, a TEAE that is both drug-related and serious, and a TEAE leading to discontinuation of study treatment will be summarized. Similar Table by BMI group ( $<30 \text{ kg/m}^2$ ,  $\geq 30 \text{ kg/m}^2$ ) will be provided. Listings will include all AEs (including participants who enrolled more than once).

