## 16. APPENDIX A

### 16.1. ALGORITHM FOR TREATMENT EMERGENCE OF ADVERSE EVENTS:

---

Document:

Author:

Version Number:

2.0

Version Date:

23APR2024

Template No.: CS\_TP\_BS016 Revision 6

Reference: CS\_WI\_BS005

Effective Date: 02Dec2019

Copyright © 2009, 2010, 2012, 2016, 2018, 2019 [REDACTED]. All rights reserved. The contents of this document are confidential and proprietary to [REDACTED] and its subsidiaries. Unauthorized use, disclosure or reproduction is strictly prohibited.

AE START DATE	AE STOP DATE	ACTION
Known	Known/Partial/ Missing	
If AE stop date is partial, impute AE stop date as latest possible date (i.e., last day of month if day unknown or 31st December if day and month are unknown).
 
If AE start date < study treatment start date, assign as pre-treatment AE.
 
If AE start date >= study treatment start date and <= study treatment stop date + 14 days, assign as TEAE.
 
If AE start date > study treatment stop date + 14 days, assign as post-treatment AE.

Partial	Known/Partial/ Missing	
If AE stop date is partial, impute AE stop date as latest possible date (i.e., last day of month if day unknown or 31st December if day and month are unknown).
 
Impute AE start date as the study treatment start date, if:
 

the year of the AE start date is equal to the year of the study treatment start date and the AE stop date is later or equal to the study treatment start date or is missing.

the year and month of the AE start date is equal to the year and month of the study treatment start date and the AE stop date is later or equal to the study treatment start date or is missing.

 
Otherwise, Impute AE start date as earliest possible date (i.e. first day of month if day unknown or 1st January if day and month are unknown). Then:
 
If AE start date < study treatment start date, assign as pre-treatment AE.
 
If AE start date >= study treatment start date and <= study treatment stop date + 14 days, assign as TEAE.
 
If AE start date > study treatment stop date + 14 days, assign as post-treatment AE.

Document: [REDACTED]

Author: [REDACTED]

Version Number:

2.0

Version Date:

23APR2024

Template No.: CS\_TP\_BS016 Revision 6

Reference: CS\_WI\_BS005

Effective Date: 02Dec2019

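### SAP 13 dates the last dose from the e-Diary alone; if diary entries stop before the tablets do, exposure is understated and the TEAE window closes early

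*SAP*

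**What the plan says.** SAP 13 uses two sources for the two ends of exposure. For the start, "The date of first study treatment administration will be taken from the Drug Accountability eCRF". For the end, "The date of last study treatment is taken from e-Diary". It has no rule for a diary that ends early, is empty, or disagrees with the eCRF.

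Protocol 6.2 provides for a second record: "Study drug start and stop dates will also be recorded in the e-Diary and eCRF". On late entries, Protocol 8.2.3.1.1 states: "The e-Diary will allow daily data entry up to 24 hours late, after which, data entry will be locked out". Protocol 8.2.3.1.3 adds a safeguard: "Sites will be contacted if 2 consecutive daily e-Diary entries are missing". The site then reminds the participant.

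SAP 15.1 ends the TEAE period 14 days after the last date of study treatment, inclusive. For an AE with a known start beyond that point, the SAP 16.1 rule ends: "study treatment stop date + 14 days, assign as post-treatment AE". Neither section says where the stop date comes from. SAP 6.5 and the footnote to Table B apply the same 14-day extension to post-baseline laboratory values and vital signs.

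**The concern.** For a woman who stops completing the diary while still taking tablets, the last e-Diary intake is the last tablet she recorded, not the last she took. The error runs in one direction: the date can only be too early. That shortens exposure and moves later AEs out of the treatment-emergent category.

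The overview, SOC/PT, discontinuation, serious, fatal and ECI summaries in SAP 15.1 count TEAEs only. After early termination this SAP analyses safety alone, and two of its endpoints are the proportion of participants with an AE and the proportion stopping treatment because of one. Elsewhere the SAP resolves doubt conservatively: an AE with unclear timing becomes treatment-emergent, missing severity becomes severe, and a missing relationship becomes related. Those rules deal with gaps in the AE record. None covers a stop date that is too early.

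**Working it through.** The plan states no figure to reproduce, so the check applies the SAP's own rule to an assumed gap.

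**Inputs**
- First tablet: Day 1. True last tablet: L = 364, that is 13 cycles × 28 days (Protocol 6.1). The days lost depend only on the gap, not on L, as long as the gap is shorter than treatment.
- Gap g: days between the last e-Diary intake and the true last tablet. The documents give no value, so g is an assumption shown as a range.
- Rule for a known AE start (SAP 16.1): TEAE if Day 1 ≤ start ≤ last dose + 14, post-treatment if later.
- Source of the last dose: the e-Diary (SAP 13). Carrying this date into 15.1 and 16.1 is an inference, because no other source is named.

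**Formulas**
- Last dose under SAP 13: D = L − g
- Window closes: D + 14, instead of L + 14 = 378
- Tablet-taking days classed as post-treatment: max(0, g − 14)
- Tail days lost: min(g, 14)
- Total window days lost: g
- Exposure: D instead of L

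| g | D (= exposure) | Window closes | Tablet-taking days lost | Tail days lost |
|---|---|---|---|---|
| 7 | 357 | 371 | 0 | 7 |
| 14 | 350 | 364 | 0 | 14 |
| 15 | 349 | 363 | 1 | 14 |
| 28 | 336 | 350 | 14 | 14 |
| 56 | 308 | 322 | 42 | 14 |
| 84 | 280 | 294 | 70 | 14 |

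For g = 28, AEs starting on Days 351–364 (tablets still taken) and Days 365–378 (true tail) are all post-treatment. With the true stop date, none of them is.

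**No diary intake.** SAP 5 admits a woman to the SAF on the Drug Accountability eCRF. If she has no e-Diary intake, SAP 13 gives no last-dose date. Her exposure cannot be computed, and an AE with a known start on or after first dose has no upper limit to be tested against.

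**Laboratory values.** V7 is scheduled 14 days after last intake, with a +5-day window, so a sample drawn on day 14 sits on the edge of the on-treatment period. A last-dose date one day too early puts it outside.

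**Compliance.** SAP 14 says "The e-Diary will be the primary source for the calculation of compliance with the use of study treatment" and divides recorded intake days by the first-to-last-dose interval. For g = 28 with every day recorded up to the gap, the e-Diary basis gives 336/336 = 100%. Moving only the denominator to the true stop date gives 336/364 = 92.3%, which counts 28 unrecorded tablets as missed even if all were taken.

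**The case against.** The e-Diary is the protocol's main record of tablet intake, and nothing shows that the eCRF stop date is independent of it or more accurate. Site alerts and reviews at visits and phone contacts make long silent gaps less likely. So does the negative home pregnancy test that must be entered in the e-Diary before each blister. All of this stands and limits how often the problem arises. None of it supplies a rule for when the two dates differ or the diary is empty.

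Several stronger readings are tempting but are not supported:

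- *Any AE on drug after the diary stops is lost.* The 14-day extension protects these AEs for gaps of 14 days or less. It also protects most AEs that cause a woman to disengage, because they start before or near her last entry.
- *The SAP says outright that TEAEs use the e-Diary date.* It does not. SAP 13 is the exposure section, and its use in 15.1 and 16.1 is a strong inference.
- *Missed entries can never be corrected.* The protocol locks the participant's entry after 24 hours. It does not rule out documented corrections.
- *Compliance is inflated.* An unrecorded day is not a missed tablet, so the e-Diary ratio is not shown to be too high.
- *Pregnancies are misclassified.* SAP 1.1 gives the clinical team the last word on their timing.
- *All laboratory results are affected.* SAP 6.3 takes the last measurement as the final value in the study, and SAP 15.3 summarises liver abnormalities over all visits. Outside the windowed by-visit values, the laboratory effect is unclear.
- *Events disappear from the report.* All AEs are listed, with post-treatment ones identified, and death details are listed separately.

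Protocol 9.4.3 counts delayed events that the investigator judges related as on-treatment, which might seem to rescue some of them. SAP 15.1 does not repeat that rule, and Protocol 9.4 lets the SAP prevail where the two differ.

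**Conclusion.** The point holds in a limited form and should be fixed. Followed as written, SAP 13 understates exposure by g days for a woman who stops recording g days before her last tablet. On the natural reading of 15.1 and 16.1, it also removes g days from her TEAE window: up to 14 tail days and max(0, g − 14) days on which she was still taking tablets. The affected AEs are those with known start dates. Many AEs with missing or partial start dates default to TEAE.

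The result rests on two assumptions: that the stop date in 15.1 and 16.1 is the SAP 13 date, and that some women have a gap. Neither the number of women nor the length of gaps can be read from the documents, so the effect on the reported proportions cannot be sized. The analysis is descriptive, and no test result depends on it.

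**What to change.** In SAP 13, define one last-dose date as the later of the last e-Diary intake and the eCRF stop date, using the eCRF date alone when there is no e-Diary intake. Name the eCRF form that holds it. Cite this date in SAP 6.5, 15.1 and 16.1, so that exposure and the TEAE and laboratory on-treatment windows share it. List the participants whose two dates differ.

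State explicitly that the SAP 14 ratio keeps the e-Diary for both numerator and denominator, or report unrecorded days separately from missed tablets. Otherwise the new date would carry into the SAP 14 denominator. Leave pregnancy timing to the clinical team's final determination.

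The cost is a wording change and a small derivation using data the protocol already plans to collect. Exposure becomes somewhat longer for participants with diary gaps. Taking the later date is a conservative choice, not proof that the eCRF is right, and the listing lets a reader judge it. Where the two sources agree, nothing changes.
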